#### 6. Treatment

#### 6.1 Treatment administered

Study drugs should be administered as soon as possible after randomization (less than 4.5h from onset of disease to onset of thrombolysis).

Thrombolysis time (intravenous infusion time in the treatment group,

intravenous infusion time in the control group, and the start and end time of intravenous infusion), administration dose (intravenous infusion dose in the treatment group, intravenous infusion dose in the control group, and intravenous infusion dose), vital signs and the occurrence of adverse events during administration should be recorded.

#### 6.2 Concomitant treatment

All enrolled subjects should be treated in the Acute Stroke Unit or, if needed, in the Intensive Care Unit (ICU). All subjects will be enrolled according to the *Chinese Guidelines for the Diagnosis and Treatment of Acute Ischemic Stroke 2018*. [28] Subsequent standardized early treatment management and secondary prophylactic medication are performed. Subjects are treated with thrombolysis according to relevant guidelines (*Chinese Guidelines for Endovascular Treatment of Acute Ischemic Stroke 2018*). [29], *Chinese Guidelines for Early Intravascular Interventional Diagnosis and Treatment of Acute Ischemic Stroke 2018*[30]), and it is up to the investigator to make the final decision on whether or not to perform endovascular treatment, and to record the treatment method and drug combination.

Concomitant drugs (including anticoagulants, defibrillators, antiplatelet agents, lipid-lowering agents, antihypertensive agents, hypoglycemic agents, etc.) before and after randomization and during hospitalization and follow-up should be recorded. Non-therapeutic drugs such as contrast agents, pre-flushing tube heparin, etc., are not recorded as concomitant drugs.

- (1) If the subject does not receive mechanical thrombotomy, no antiplatelet drugs, anticoagulants, defibrillators, thrombolytic drugs or drugs that may affect platelet and clotting function are allowed to be used within 24 hours after the study drugs is used.
- (2) If the subjects have received mechanical thrombotomy but do not receive emergency stent implantation, the investigators will determine whether the concomitant use of antiplatelet and anticoagulant therapy is necessary according to relevant guidelines within 24h after the use of the study drugs, and the concomitant use of drugs will be recorded.
- (3) If the subjects have received emergency stent implantation, antiplatelet agents and anticoagulants can be used within 24 hours after the study drugs is used.
- (4) Any medication other than those listed above (including blood pressure lowering, blood glucose lowering, lipid-lowering drugs, etc.) is allowed. If necessary,

the investigator should carefully consider administering a relatively stable and safe dose to the subject.

During the study period, any treatment and/or prescriptions issued prior to randomization or any medication changes during the study period should be recorded on an electronic case report form.

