#### 4.4 Removal criteria

- 1) Cases who are found not meeting the inclusion criteria or meeting the exclusion criteria after enrollment;
- Cases to be removed due to violation of the provisions of the clinical trial protocol for concomitant medication and/or treatment, as determined by the Academic Committee;
- 3) Cases without medication after enrollment;
- 4) Cases without evaluable records after administration;
- 5) Cases who fail to take stipulated medication with poor compliance, resulting in impossibility to judge efficacy or incomplete data adversely affecting the judgment of efficacy and safety.

Cases eliminated should be explained, and their data should be kept complete for future reference. If patients have received at least one study drug treatment, ITT analysis could be performed according to the data records. Patients who have received at least one treatment and have a safety record may also be included in the safety analysis as appropriate.

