## 9.7 Emergency response plan for adverse events

## 1) Bleeding event management plan

In order to prevent the occurrence of bleeding events, the inclusion and exclusion criteria of this study protocol should be strictly followed to exclude the subjects with potential high blood risk. During thrombolytic therapy, close attention should be paid to the changes of symptoms and signs of subjects so as to detect bleeding events in time. The treatment of bleeding events should follow the clinical routine of the hospital and be based on the clinical judgment of doctors. The following measures can be referred to:

- 1. If the patient has neurological symptoms and/or abnormal signs within 24 hours after the start of treatment, intracranial hemorrhage should be suspected, and the thrombolytic, antiplatelet and anticoagulant drugs being used should be discontinued, and imaging examination should be performed immediately to confirm the site of bleeding;
- 2. If intracranial hemorrhage or other clinically visible bleeding (such as hematemesis, hematochezia, hemoptysis, etc.) is confirmed, the following measures are recommended:
  - (1) Completely discontinue thrombolytic, antiplatelet and anticoagulant drugs;
- (2) Invite relevant professional physicians for consultation to jointly determine the symptomatic treatment plan;
  - (3) Closely monitor the vital signs and timely treat complications;
  - (4) Fresh frozen plasma infusion;
- (5) Use antifibrinolytic drugs such as tranexamic acid within 24 hours after thrombolytic therapy.
  - (6) If normal heparin therapy is used at the same time, protamine may be used within 4 hours to exert an antagonistic effect of heparin (1mg of protamine to antagonize 100U of normal heparin);
  - (7) Blood transfusion: Blood transfusion may be required to correct hemodynamic abnormalities (hypotension caused by bleeding) or anemia. The indications for blood transfusion should be mastered according to the clinical judgment of the doctor. While strictly grasping the indications for blood transfusion, attention should be paid to the adverse effects of severe anemia on acute myocardial infarction.
  - (8) Evaluate the feasibility of surgical intervention when necessary;
- 3. Minor bleeding, such as skin and mucosal bleeding, nosebleed, gingival bleeding, microscopic hematuria, positive stool occult blood, etc., can be symptomatic in advance,

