and thrombolysis, antiplatelet and anticoagulant therapy should be continued according to the bleeding degree.

In particular, symptomatic intracranial hemorrhage (2%-7%). The vast majority of symptomatic intracranial hemorrhage occur within 24 hours of thrombolytic therapy. The symptoms include sudden changes in the state of consciousness, single or multiple location signs of the nervous system, coma, headache, nausea, vomiting and seizures, hypertensive emergency, and rapid death in some cases. When this happens, active measures should be taken:

- (1) Stop thrombolysis, antiplatelet and anticoagulant therapy immediately.
- (2) Perform imaging examination (emergency CT or MRI) to determine the location, amount and classification of intracranial bleeding.
  - (3) Measure erythrocyte volume, hemoglobin, prothrombin, activated partial thromboplastin time, platelet count, fibrinogen, D-dimer, blood group and perform a cross-match test.
  - (4) Reduce intracranial pressure, including proper control of blood pressure, raising the head of the bed by 30 degrees, intravenous mannitol, endotracheal intubation and auxiliary ventilation, surgical hematoma removal, decompression of bone flap and ventricle puncture and drainage when necessary.
  - (5) If necessary, use reverse thrombolysis, antiplatelet and anticoagulant drugs: 2U of fresh frozen plasma should be given every 6 hours within 24h; it is recommended to neutralize with protamine (1mg protamine to neutralize 100U of normal heparin) for patients who have used normal heparin therapy within 4h. If the bleeding time is abnormal, 6-8U of platelets can be transfused.
  - (6) Properly control the blood pressure.

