#### 12. Statistical plan

## 12.1 Statistical analysis

Full analysis set (FAS), per protocol set (PPS) and safety analysis set (SAS) will be established according to the NMPA regulations for data statistical analysis. Strict quality control will be carried out in the whole process of data collection to ensure the authenticity of the evaluation data.

Full analysis set (FAS): a data set consisting of all subjects randomized to receive at least one study drug according to the basic principle of Intention To Treat.

Per protocol set (PPS): PPS includes all subjects who complete the stipulated treatment without missing primary efficacy endpoints or serious violations of the protocol. Serious protocol violation will be finally defined during data review and

may generally include (but not limited to) the following situations: subjects violating inclusion criteria or exclusion criteria, poor compliance in stipulated medication, concomitant medication that affects outcome indicators, and out of visit window.

Safety analysis set (SS): a set of all subjects participating in the trial, receiving at least one study drug, and having at least one safety evaluation.

FAS and PPS are established as sensitive analysis groups; Efficacy analysis is performed on the basis of FAS and PPS. Safety endpoints will be performed on the safety set and safety missing data will not be filled. All baseline demographic data analyses will be performed on the basis of the FAS; illogic data needs to be investigated by the data management facility, investigators or Sponsor together to identify possible reasons, and restrained by the parties in a data review meeting after full discussion: illogic data, if sufficient reasons have been found to indicate its incorrectness, should be removed, or otherwise, should be remained and subjected to analysis and the results obtained without such removed data should be treated as sensitivity analysis; If there is data collected in the study that is not in accordance with the program requirements such as planned external visits, it will be presented in a list, and descriptive or comparative analysis will be decided at the data review meeting depending on the specific situation of the data.

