#### **Protocol Deviations**

Participant data will be examined for evidence of protocol violators in order to assess how well the protocol was followed. Inclusion and exclusion criteria are detailed in the study protocol.

Participants who commit protocol violations will be included in the FAS Population but

excluded from the Per Protocol Population. These protocol violations will be shown in a listing. Patients can either be full or partial protocol violators. A full protocol violator is completely excluded from the Per Protocol Population. A partial protocol violator has only some data excluded. For those who violated the protocol during the treatment period due to unpermitted changes in the medication or prohibited concurrent medication, the analysis will only use data recorded prior to the violation. For all violations which reference the treatment period, the treatment start date will be used as the reference date.

A listing of all possible protocol violators will be produced for clinical review. The final list of patients who are protocol violators and are therefore excluded from the Per-Protocol population will be agreed by the study team.

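### Section 6.2(1) bars clotting-active drugs for 24 hours with no exception for bleeding, section 9.7 lists such drugs for a bleed, and the SAP's violation rule could then drop these patients' day-90 mRS from the per-protocol set

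*Supplement*

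**What the plan says.** **Concomitant-drug rule.** Final protocol section 6.2(1) opens with a condition, "If the subject does not receive mechanical thrombotomy", and then states that "no antiplatelet drugs, anticoagulants, defibrillators, thrombolytic drugs or drugs that may affect platelet and clotting function are allowed to be used within 24 hours" after study drug. Items (2) and (3) relax the rule on antiplatelets and anticoagulants after thrombectomy or emergency stenting. No item mentions treatment of a bleed.

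**Bleeding plan.** Section 9.7 offers measures that sites may refer to once intracranial or other visible bleeding is confirmed. One is "Use antifibrinolytic drugs such as tranexamic acid within 24 hours after thrombolytic therapy". The measures for symptomatic intracranial hemorrhage (sICH) add, where necessary, that "2U of fresh frozen plasma should be given every 6 hours within 24h", and then "If the bleeding time is abnormal, 6-8U of platelets can be transfused". The same section puts sICH at 2%-7% and says that most of it occurs within 24 hours of thrombolysis.

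**Analysis rules.**
- Protocol section 4.4(2) lists "Cases to be removed due to violation of the provisions of the clinical trial protocol for concomitant medication and/or treatment", subject to a determination by the Academic Committee.
- Protocol section 12.1 gives "concomitant medication that affects outcome indicators" as one example of a serious violation that keeps a patient out of the PPS. The definition is finalised at data review.
- Final SAP section 7 speaks of concomitant treatment that seriously interferes with the efficacy evaluation, also finalised at data review.
- Final SAP section 11 (Protocol Deviations) says, for patients with "prohibited concurrent medication, the analysis will only use data recorded prior to the violation". Violators stay in the FAS, and the study team agrees the final list.
- Final SAP section 12 runs the primary efficacy analysis on both the FAS and the PPS.

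**The concern.** An antifibrinolytic is, on its face, a drug that may affect clotting function, and both passages use a 24-hour window from thrombolysis. A site that follows section 9.7 for a first-day bleed therefore breaches the wording of section 6.2(1). Because exclusion criterion 1 removes patients scheduled for endovascular therapy, the group without thrombectomy should be most of the trial.

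The analysis rules then attach a consequence to that breach. If the drug counts as prohibited concurrent medication, SAP section 11 uses only earlier data. For a bleed on day 1, that leaves no day-90 mRS for the PPS. The exclusion would be triggered by an event after randomization that the study drug itself can cause, in patients who are likely to have a poor outcome. Fixing PPS membership before unblinding, as the SAP plans, does not remove this: reviewers masked to treatment would still exclude patients at whatever rate each drug leads to treated bleeding.

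**Working it through.** **Step 1: the passages side by side.**

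| Agent in 9.7 | Stated window | Conflict with 6.2(1)? |
|---|---|---|
| Antifibrinolytics | Within 24 h after thrombolysis | Yes, same window |
| Fresh frozen plasma | Within 24 h, starting point not stated | Yes on a plain reading, if plasma counts as a drug |
| Platelets | None stated | Not established |
| Protamine | Tied to heparin use | Adds no new violator: the heparin is already an anticoagulant barred by 6.2(1) |

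The antifibrinolytic line alone is enough for the contradiction.

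**Step 2: the plan's own figures.** Inputs from protocol section 11: margin 0.937, control rate 59.32%, RR 1.07, one-sided alpha 0.025, power 0.85, dropout 10%.
- Margin: 1.14^(-0.5) = 0.9366, stated as 0.937.
- n per arm = (1.960 + 1.036)² × [(1-p1)/p1 + (1-p0)/p0] / [ln(1.07/0.937)]², with p0 = 0.5932 and p1 = 1.07 × p0. This gives 642.8, against 642 stated.
- 643/0.9 = 714.4, rounded up to 715 per arm, as stated.

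**Step 3: effect on the PPS.** Put the truth at the margin: pc = 0.5932 and pt = 0.937 × 0.5932 = 0.5558, with 642 per arm. Assume that shares bt (test) and bc (control) are dropped and that all of them have mRS above 1. The documents give neither share.
- PPS rates: pt/(1-bt) and pc/(1-bc).
- PPS RR = 0.937 × (1-bc)/(1-bt).
- SE of log RR = sqrt[(1-qt)/(qt·nt) + (1-qc)/(qc·nc)], where qt and qc are the PPS rates, nt = 642(1-bt) and nc = 642(1-bc).
- PPS-only one-sided error = P(Z > 1.96 - ln(RR_PPS/0.937)/SE).

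| Dropped, test v control | PPS RR | PPS-only error |
|---|---|---|
| 2% v 2% | 0.937 | 2.5% |
| 3% v 2% | 0.947 | 4.1% |
| 2% v 3% | 0.927 | 1.5% |
| 4% v 2% | 0.957 | 6.4% |
| 2% v 4% | 0.918 | 0.8% |
| 7% v 2% | 0.987 | 20% |

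For 3% v 2%: ln(0.9467/0.937) = 0.0103, SE = 0.0473, shift 0.217, so P(Z > 1.743) = 4.1%. If 10% of those dropped had mRS 0-1, the errors for 3% v 2% and 7% v 2% fall to 3.7% and 15%.

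For scale, the protocol's 2%-7% sICH range is 0.02 × 642 = 13 to 0.07 × 642 = 45 patients per arm. Not all of them would have received a clotting-active drug within 24 hours.

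**Step 4: if both sets must succeed.** Simulating the FAS and PPS tests together (400,000 runs per scenario, true RR at the margin) gives a joint error of about 2.5% for 3% v 2% and for 7% v 2%. When the test arm loses more failures, the FAS test is the binding one.

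**The case against.** The strongest reply has four parts.

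1. **Scope of the ban.** The wording in 6.2(1) follows a list of mainly antithrombotic classes, so the closing phrase may mean similar drugs and not agents used to treat a bleed. Section 9.7 is the specific rule for bleeding, defers to hospital routine and clinical judgement, and offers its measures for reference. This is a fair reading, but nothing in the text states it, and the literal words say otherwise. A reader might infer that sites are forbidden to treat a bleed; the documents do not go that far. They are inconsistent.

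2. **No automatic exclusion.** A reader might infer that every patient treated for an early bleed becomes a violator and leaves the PPS. The documents do not support that. Removal under 4.4(2) is for the Academic Committee, the definition of a serious violation is left to data review, and the study team agrees the list. The SAP also ties its data cut-off to violations during the treatment period, which it does not define for a single-dose drug. This objection stands in full. What remains is that no passage protects these patients and that the letter of SAP section 11 points towards discarding their outcome.

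3. **Direction.** A reader might infer a bias towards non-inferiority. That needs more treated bleeds on tenecteplase. The comparative sICH figures at 0.25 mg/kg in protocol section 1.3 show no such excess: 1/52 v 2/51 in ATTEST and 1% in each arm of EXTEND-IA TNK Part 1. The 2%-7% range in section 9.7 is not split by drug. This stands: the direction is unknown.

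4. **The FAS.** It keeps these patients, and no passage lets the PPS alone establish non-inferiority. This stands too.

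**Conclusion.** The contradiction between sections 6.2(1) and 9.7 is real in the final protocol, at least for antifibrinolytics and on a plain reading for plasma, in patients without thrombectomy. Its analysis consequence is a possibility left open by the text: the day-90 mRS of patients treated for an early bleed could be lost from the PPS.

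The size depends on assumptions that the documents cannot settle: the share treated with a clotting-active drug within 24 hours, the share then excluded, their outcomes, and above all a difference between arms. Equal rates give no bias. A one-point difference moves the PPS-only error to 4.1% or 1.5%, depending on which arm loses more. The 20% figure sets the test drug at the top and the control at the bottom of the sICH range and should be read as an extreme bound. None of these figures is the trial's false-positive rate if the FAS and PPS must both succeed; the documents do not say whether they must. The point merits correction because the outcome-discarding rule is tied to a possible harm of the study drug, and the remedy costs almost nothing.

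**What to change.** - Reconcile section 6.2(1) with the bleeding plan in section 9.7 so that the two no longer contradict each other. Which clinical rule should prevail is for the sponsor and investigators.
- Before database lock, state in protocol sections 4.4(2) and 12.1 and in SAP sections 7 and 11 that, for analysis purposes, treatment given for a bleeding event after study drug does not by itself exclude a patient from the PPS and does not discard the day-90 mRS.

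The cost is a few sentences, with no new data and no further patients. The PPS result may become slightly less favourable, since patients with likely poor outcomes stay in it.

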### 6.3 Medication compliance

In the recruitment and screening stage, the purpose of the trial, the basic information of the study drugs, the protocol, the trial process, the administration regimens, clinical observation, the potential risk if participating in the study, compensation, etc., will be introduced in detail, so that subjects could be fully informed and voluntarily participate in the study to improve the compliance of the study. This study uses single dose, to be administered by the study nurse. Before administration, subject number, administration table and dosage should be carefully checked; after administration, the remaining quantity of study drugs, empty packages and administration equipment should be carefully checked.

## 7. Study process

## 7.1 Screening/baseline assessment

- 1) Demographic information: sex, age, ethnicity.
- 10) The time of present onset as well as the symptoms (the present onset symptoms are mainly reflected in NIHSS score).
- 11) Risk factors (past medical history and history of present illness): high blood pressure, diabetes, cerebral infarction, TIA, coronary heart disease, myocardial infarction, arrhythmia, always oral medication (aspirin, clopidogrel, and warfarin, antihypertensive drugs, lipid-lowering drugs, oral glucose-lowering drugs, drug adjust heart rate), dementia, peripheral artery disease, lipid metabolic disorders, liver and kidney function is not complete, and neck intracranial vascular stenosis or deformity, smoking, drinking alcohol.
- 12) Prior and concomitant medication.
- 13) Vital signs (blood pressure, pulse, respiratory rate and body temperature).

- 14) MRS score before onset, MRS score post onset before onset of thrombolysis, NIHSS score post onset before onset of thrombolysis.
- 15) Electrocardiogram (If the subject has had an electrocardiogram before thrombolysis after the onset of the disease, no repeat examination is required).
- 16) Imaging (CT or MRI).

Screening/baseline imaging examination is "CT or MRI", which is used to exclude hemorrhagic stroke; the CT or MRI results generated by other hospitals can also be used as a screening basis, if the study physician deems them acceptable; if a subject has undergone a CT or MRI check post symptom onset before onset of thrombolysis, such examination may be omitted. CT or MRI evaluation should include: cerebral hemorrhage, acute severe symptomatic ischemia in the area of blood supply, or other pathological changes.

### 17) Laboratory examination:

### **Routine blood test:**

Red blood cell count (RBC), white blood cell count (WBC), neutrophil count (NEU), lymphocyte count (LY), hematocrit (HCT), hemoglobin (Hb), platelet count (PLT);

## **Blood biochemistry:**

Creatinine (GREA), UREA (or blood urea nitrogen BUN), glucose (GLU), uric acid (UA), lactate dehydrogenase (LDH), creatine phosphokinase isoenzyme (CK-MB), alkaline phosphatase (ALP), glutamyltranspeptidase (GGT), aspartate aminotransferase (AST), alanine aminotransferase (ALT), total cholesterol (TC), low density lipoprotein (LDL-C), high density lipoprotein (HDL-C), triglyceride (TG);

For baseline blood lipid tests (total cholesterol (TC), low density lipoprotein (LDL-C), high density lipoprotein (HDL-C), triglyceride (TG)), the most recent fasting blood lipid after the onset of the disease should be measured. Blood glucose test is performed at baseline using peripheral blood glucose measured in venous blood as one of the inclusion and exclusion criteria;

